#### **8.11.5 Resting 12-lead ECG**

A 12-lead ECG will be obtained after the subject has been resting in the supine position for at least 5 minutes, at time points outlined in the Section 2.1.2 (Baseline, Week 6). All ECGs will be documented by recording date, time of collection, all abnormal wave form noted, ventricular rate, all intervals including PR, RR, QRS, QT and QTcF ("12-Lead ECG" CRF section). ECG abnormalities are signed as 'Yes' on 'Clinically significant findings' field of the "12-Lead ECG" section.

#### **8.11.6 Physical examination**

A physical examination will be performed at Screening, Week 6 and Week 10 and collected in "Physical Examination" CRF section. Physical examination includes body weight, height, BMI, vital signs and an assessment of the following: general appearance, skin, head and neck, lymph nodes, thyroid, abdomen, musculoskeletal, cardiovascular, respiratory, and neurological systems.

#### **8.11.7 Columbia-Suicide Severity Rating Scale**

Columbia-Suicide Severity Rating Scale is collected at Screening (C-SSRS SCN CRF page) at Baseline, Week 2 D8, Week 2 D12, Week 3 D15, Week 3 D19, Week 4 D22, Week 4 D26, Week 5 D29, Week 5 D33, Week 6 D36, Week 6 D40, Week 10 Follow-up/Final visit for withdrawals (C-SSRS-SLV CRF page).

### **9 ANALYSIS SETS, GROUPS AND SUBGROUPS**

#### **9.1 ANALYSIS SETS**

Different analysis sets will be planned for the analyses and all will be identified and finalized before the database is locked. Subjects without valid written study informed consent will be excluded from all analysis sets.

The following analysis sets are defined for the statistical analysis:

- **Screened set (SCR)** - All subjects with signed written informed consent and a subject identification number;
- **Randomized set (RAN)** – All subjects who received a randomization number, regardless of receiving trial medication;
- **Safety set (SAF)** – All subjects who received the double-blind study drug. Subjects will be analyzed according to treatment received;
- **Full Analysis set (FAS)** – All subjects in RAN who were not mis-randomized (Mis-randomized subjects are those who have not been qualified for randomization or who have been inadvertently randomized into the study but have not received double-blind study drug). Following the intent-to-treat (ITT) principle, subjects will be analyzed according to the treatment they have been assigned to at the randomization;
- **Per Protocol set (PPS)** – All subjects in FAS who took the study medication and had no major protocol deviations;
- **Pharmacokinetic Analysis set (PKS)** – The PKS will include all subjects who receive a

dose of MM-120 and have at least 1 post-dose PK measurement without major protocol deviations or violations thought to significantly affect the PK of the drug. Data from subjects with deviations determined to affect PK will be excluded from the PKS. Subjects that receive placebo will not be part of the PK analysis set. Subjects will be analyzed according to the treatment they actually received.

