5.2 Procedures for Handling Incorrectly Randomized Subjects

Subjects who fail to meet the inclusion/exclusion criteria should not, under any circumstances, be randomized into the study. There can be no exceptions to this rule.

A subject who does not meet the eligibility criteria but who is randomized in error, and is identified before dosing, should be withdrawn from the study and another subject should be enrolled and receive the same treatment.

Sponsor's Medical Monitor should be notified if an ineligible subject is dosed.

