13.2 Analysis Sets

The following analysis sets will be defined for the statistical analysis. Subjects without valid written study informed consent will be excluded from all analysis sets.

- **Randomized set (RAN)** – All subjects who received a randomization number, regardless of receiving trial medication.
- **Safety set (SAF)** – All subjects who received the double-blind study drug. Subjects will be analyzed according to treatment received.
- **Full analysis set (FAS)** – All subjects in RAN who were not mis-randomized
 - † Following the intent-to-treat (ITT) principle, subjects are analyzed according to the treatment they have been assigned to at the randomization.
 - † Mis-randomized subjects are those who have not been qualified for randomization and who have been inadvertently randomized into the study but have not received double-blind study drug.
- **Per protocol set (PPS)** – All subjects in FAS who took the study medication and had no major protocol deviations
- **Pharmacokinetic analysis set (PKAS)** – The PK analysis set will include all participants who receive a dose of MM-120 and have at least 1 postdose PK measurement without important protocol deviations or violations thought to significantly affect the PK of the drug. Data from participants with deviations determined to affect PK will be excluded from the PK analysis set. Participants that receive placebo will not be part of the PK analysis set. A strategy for dealing with data affected by protocol violations and deviations will be agreed to by the Sponsor, monitor, and pharmacokineticist, prior to clean file and code break. Participants will be analyzed according to the treatment they actually received.
 - ‡ Subjects will be analyzed according to the treatment received.
 - ‡ Major protocol deviations are those affecting the primary endpoint analyses and will be finalized prior to unblinding treatment codes for analyses. A list will be provided in the Clinical Study Report Statistical Analysis Plan.

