#### **10.7 PRIMARY EFFICACY ENDPOINT**

The primary analysis will be performed according to the intent-to-treat (ITT) principle on the FAS.

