### 10.7.2 Main analysis

#### 10.7.2.1 Estimand

The primary estimand quantifies the treatment effect of MM-120 at 6-weeks vs placebo after twice weekly administration while accounting for intercurrent events (IEs) with potential confounding effects and IEs leading to study discontinuation prior to the 6-week assessment.

The following attributes describe the primary estimand:

- Population: Subjects in the FAS
- Endpoint: Change from baseline to Week 6 in the AISRS Score
- Treatment of interest: the randomized treatment MM-120 or placebo as a twice weekly treatment.
- Handling of intercurrent events (IEs) prior to AISRS assessments.

Depending on the IE causing the missing or potentially biased value, two sequential policy strategies will be applied:

1. Policy strategy. Available data will be used; missing data will be imputed under a Missing At Random (MAR) assumption by borrowing information from subjects in the same treatment group in following cases:
  - IEs related to COVID-19 pandemic and other intercurrent missing data (see details in Section 10.7.2.1.1).
2. Policy strategy. Available data recorded after the IE will be set to missing; such missing data will be imputed/substituted under a Missing Not At Random (MNAR) assumption by borrowing information from the placebo arm subjects (reference-based imputation) in following cases:
  - Intake of prohibited medications/therapies with potential confounding effect (APPENDIX C) (see details in Section 10.7.2.1.1).
  - Other IEs leading to treatment/study discontinuation (except those related to COVID-19 pandemic (see details in Section 10.7.2.1.1)).

- Summary measure: Difference between MM-120 and placebo in mean change from baseline to Week 6 for AISRS Score.

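### SAP 9.1 replaces the protocol's *and* with *or* in defining mis-randomized subjects, so it is unclear whether ineligible but dosed subjects stay in the primary analysis set

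*SAP*

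**What the plan says.** Both documents define the FAS as the randomized set less the mis-randomized; in the SAP's words, "All subjects in RAN who were not mis-randomized". They differ on who is mis-randomized.

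- Protocol 13.2: "Mis-randomized subjects are those who have not been qualified for randomization and who have been inadvertently randomized into the study".
- SAP 9.1: "Mis-randomized subjects are those who have not been qualified for randomization or who have been inadvertently randomized into the study".

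Each sentence then closes with the same no-drug condition: the subject was never given the blinded treatment.

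The FAS carries the main result. SAP 10.7 states: "The primary analysis will be performed according to the intent-to-treat (ITT) principle on the FAS". The estimand in SAP 10.7.2.1 takes its population from the same set: "Population: Subjects in the FAS".

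Protocol 5.2 treats ineligible subjects differently before and after dosing. A subject randomized in error who "is identified before dosing, should be withdrawn from the study and another subject should be enrolled and receive the same treatment". If an ineligible subject has already been dosed, that section asks only that the Sponsor's Medical Monitor be told.

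SAP Appendix D, which lists departures from the protocol's analyses, records the addition of a Screened set but not this change. The version history in Appendix B does not mention it either.

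**The concern.** One conjunction decides who is in the primary analysis. Under the protocol, a subject who has taken study drug can never be mis-randomized. In the SAP the relative clause restarts after *or*, so the no-drug condition attaches most naturally to the second half of the sentence alone. Failing eligibility then becomes sufficient for removal, whether or not the subject was dosed.

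A subject removed this way would appear in no planned efficacy analysis. The sensitivity analyses in SAP 10.7.3 and 12.4.2 run on the FAS or on the Per Protocol Set, which is a subset of the FAS. The key secondary and other secondary endpoints also use the FAS. The planned tables give counts of FAS exclusions (Layout T1), but the violations listing covers reasons for leaving the Per Protocol and PK sets only.

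Some eligibility criteria, such as exclusions 3 and 16, rest on the investigator's opinion. A later finding that a subject never qualified can therefore involve discretion.

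**Working it through.** **Step 1: apply each wording to every case.** Let I = ineligible, A = inadvertently randomized, D = dosed. Mis-randomized means:

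- Protocol 13.2: I and A and not D.
- SAP, more natural reading: I or (A and not D).
- SAP, second reading: (I or A) and not D.

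| Subject | Protocol | SAP, more natural reading | SAP, second reading |
|---|---|---|---|
| Ineligible, inadvertently randomized, dosed | in FAS | **out** | in FAS |
| Ineligible, inadvertently randomized, not dosed | out | out | out |
| Eligible, inadvertently randomized, not dosed | in FAS | **out** | **out** |
| Eligible, inadvertently randomized, dosed | in FAS | in FAS | in FAS |
| Ineligible, not inadvertently randomized, dosed | in FAS | **out** | in FAS |
| Ineligible, not inadvertently randomized, not dosed | in FAS | **out** | **out** |

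Eligible subjects randomized as intended are in the FAS under all three. Bold marks a departure from the protocol. The two SAP readings disagree only about dosed ineligible subjects. Neither reading matches the protocol in every row: an eligible subject randomized inadvertently and not dosed is lost under both.

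**Step 2: reproduce the design figure.** Protocol 13.6.4 gives 26 per arm, standardized effect d = 0.60, one-sided 0.10 and 80% power. For a two-sample t-test:

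- df = n1 + n2 − 2 = 50
- noncentrality = d / √(1/n1 + 1/n2) = 0.60 / √(2/26) = 0.60 / 0.2774 = 2.163
- power = P(noncentral t > the 0.90 quantile of t on 50 df) = 0.806

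The normal approximation gives 0.811. Both agree with the stated 80%.

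**Step 3: remove dosed subjects.** The documents give no count, so the number lost is an assumption.

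| Subjects lost | Split between arms | All from one arm |
|---|---|---|
| 0 | 0.806 | 0.806 |
| 1 | 0.800 | 0.800 |
| 2 | 0.794 | 0.794 |
| 4 | 0.782 | 0.780 |
| 6 | 0.769 | 0.763 |

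Each subject is 1/52 = 1.9% of the planned set.

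**Step 4: influence of one subject on the estimate (illustration).** Suppose the removed subject lies 2 SD from the mean of a 26-subject arm. That mean moves by 2/25 = 0.08 SD. The smallest observed effect reaching one-sided p < 0.10 is 0.38 in the protocol, and 0.36 by the t calculation at 26 per arm. The shift is 0.08/0.38 = 21% or 0.08/0.36 = 22% of that threshold. This shows how far one exclusion can move the result; it is not an estimate of bias.

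**The case against.** The best case on the other side is that the *or* is a slip and nothing was meant to change. Appendix D declares the one analysis-set addition and is silent on the FAS. Protocol 5.2 ties withdrawal and replacement to discovery before dosing. The Per Protocol Set already exists to remove dosed subjects with major deviations. All of this favours the second reading for dosed subjects. It is suggestive rather than decisive, and it leaves the published rule open to two populations.

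A reader might infer that the primary comparison is biased. The documents do not support that. Eligibility rests on facts from before randomization, checked at screening and baseline. Excluding on them while blinded does not by itself bias the comparison, and neither does an uneven count between arms. Bias needs selection related to both treatment and outcome. SAP 9.1 also requires the sets to be finalized before database lock, and SAP section 4 requires the protocol violation database to be locked before the analysis is run. These safeguards stand, but they are not complete. Blinded Week 6 scores can be known before lock, and protocol 11.2 allows treatment-revealing data to be added after clean file but before the final lock.

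A reader might also infer that the ITT principle is simply broken. In SAP 9.1 the ITT statement is a separate sentence about analysing subjects as assigned, and the protocol's own FAS drops some undosed randomized subjects under the same label.

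**Conclusion.** The point holds as a defect in a rule that defines the primary population. The SAP departs from the protocol without recording it. On the more natural reading, failing eligibility removes a subject from the FAS even after dosing; on the second reading it does not. One difference does not depend on the reading: eligible subjects inadvertently randomized and never dosed are removed by the SAP and kept by the protocol.

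The known effect is small. The documents do not say that any subject is affected, and the protocol allows no eligibility exceptions, so the number may be zero. Losing one per arm costs about one percentage point of power (0.806 to 0.794), assuming d = 0.60 and a simple two-sample t-test. What matters is the room for discretionary exclusion after randomization in a trial planned for 52 subjects, which finalizing the sets before lock reduces but does not close.

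The documents do not show that dosed subjects were excluded, that the change was deliberate, or that the result is biased.

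**What to change.** Restore the protocol 13.2 sentence in SAP 9.1, which begins "Mis-randomized subjects are those who have not been qualified for randomization and who have been inadvertently randomized into the study" and goes on to limit the definition to subjects never given the blinded treatment. Every dosed subject then stays in the FAS, and the set again matches the split in protocol 5.2. If a change was intended, state it explicitly and list it in Appendix D.

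If the sets are already fixed, state in the clinical study report which reading was applied and whether any dosed subject was left out of the FAS.

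The cost is one word in the SAP, or a short statement in the report. No new data or analyses are needed.

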## 9.2 GROUPS

Two randomized treatment groups will be used in all statistical analyses defined in this SAP (unless explicitly specified):

- MM-120 (D-lysergic acid diethylamide D-tartrate (LSD); refer to definition of the Arm 2-MM-120 in Section 2.1.1 );
- Placebo (refer to definition of the Arm 1-Placebo in Section 2.1.1)

## 9.3 SUBGROUPS

Primary endpoint main analysis will be performed on the following subgroup populations:

**1. Severe ADHD:** Adult Attention Deficit Investigator Symptom Rating Scale (AISRS) score of  $\geq 38$  at baseline.

**2. Moderate ADHD:** Adult Attention Deficit Investigator Symptom Rating Scale (AISRS) score of  $< 38$  at baseline.

## 10 STATISTICAL ANALYSIS

### 10.1 GENERAL STATISTICAL METHODOLOGY

Unless otherwise specified:

- Parameters will be shown in tables and listings according to the CRF order;
- In summary tables, all subjects will be grouped by treatment group; the 'LSD' treatment group will be displayed in the first column and 'Placebo' in the second; a 'total' column (including the two treatment groups) may be added in some tables as specified in TLF layouts section;
- Continuous numerical variables will be summarized using the following descriptive statistics: n, mean, standard deviation (SD), median,  $Q_1$  (25th percentile),  $Q_3$  (75th percentile), minimum, and maximum;
- Categorical including ordinal variables will be summarized by frequency and incidence;
- All statistical tests (unless explicitly specified) will be carried out at a significant level ( $\alpha$  level) of 0.05, two-tailed 95% Confidence Interval (CI) will be reported.
- Listings include data from scheduled and unscheduled assessments;
- All listing will be ordered by Treatment, Subject ID, visit/date/time (where applicable).

### 10.2 SUBJECT DISPOSITION, PROTOCOL VIOLATIONS AND TRIAL TERMINATION

- Counts and percentages of subjects included and excluded from each analysis set will be provided.

- A summary of the subject disposition will be provided including the following variables, for the SCR:
  - Subjects screened;
  - Screen failures (screened, but not randomized);
  - Subjects randomized;
  - Subjects treated (who received at least one dose);
  - Subjects who prematurely discontinued the study and reasons;
  - Subjects who completed the study.

A listing of subjects' disposition will be provided, based on SCR set.

- Violations leading to exclusion from the PPS and PKS analysis sets will be listed.

## 10.3 SUBJECT CHARACTERISTICS

### 10.3.1 Demographic characteristics

Summary statistics (see Section 10.1) will be summarized by treatment group and overall for all the demographics characteristics (see Section 8.1.1); these summaries will be performed on the FAS.

Demographics will be listed on FAS.

### 10.3.2 Baseline disease characteristics

Baseline disease characteristics (Section 8.1.2) will be summarized by treatment group and overall, on the FAS, using descriptive statistics for continuous and categorical data.

### 10.3.3 Medical history and concomitant diseases

Medical history and concomitant diseases (section 8.3) will be summarized separately, displaying counts and percentages of subjects having experienced at least one prior or concomitant disease. Counts and percentages of subjects having experienced at least one prior or concomitant disease will be presented by system organ class (SOC) and individual preferred term within each SOC as well as by individual preferred term. The summary tables will be presented in descending order according to their incidence in the active treatment group (e.g., SOC and individual preferred term within each SOC with the highest number of occurrences appear first); ties will be sorted alphabetically.

The counting of the diseases is handled as follows:

- Subjects with two occurrences of the same disease (as qualified by its preferred term(s)) will be counted only once;
- In case the reported disease will be assigned to several preferred terms, subjects will be counted for each individual preferred term.

Previous conditions will be reported separately from concomitant ones.

Individual subjects' listings of previous and concomitant diseases will be provided separately on the FAS.

ADHD medical history will be summarized and listed separately on the FAS.

### 10.3.4 Previous and concomitant medications

Individual subject listing will be provided on the FAS.

Previous and concomitant medications (Section 8.4) will be summarized displaying counts and percentages of subjects having taken at least one treatment. A specific summary for previous and concomitant ADHD medication will be provided.

Counts and percentages of subjects having taken at least one treatment will be presented by Anatomic Therapeutic Chemical (ATC) class 3 and individual preferred term within each ATC as well as by individual preferred term. The summary tables will be presented in descending order according to their incidence in the active treatment group (e.g., ATC and individual preferred term within each ATC with the highest number of occurrences appear first) sorting ties alphabetically.

The counting of the medications will be handled as follows:

- Subjects who took more than once the same medication (as qualified by its preferred term(s)) will be counted only once;
- In case the reported medication is assigned to several preferred terms, subjects will be counted for each individual preferred term.

Prohibited medications will be flagged in the listing with the concomitant medications and will be summarized separately as defined for concomitant medications above. Final list with prohibited medications will be provided by the Sponsor.

#### **10.3.5 Cognitive Performance Tests (Computer Test)**

Tests are performed at Baseline and Week 6 (prior to last dose).

Frequency statistics will be provided for 'Stop Signal Task', 'Discounting Task', 'Psychomotor Vigilance Task', 'Time Production Task' and 'Time Reproduction Task' categories at Baseline and Week 6 for FAS population.

Additionally, the number (%) of completers and non-completers of the test will will be evaluated by the answer 'Yes|No' to the question Cognitive performance tests performed? respectively and will be presented in the summary table. The data are collected in the 'Cognitive Performance Tests' sections at baseline and Week 6.

A listing with cognitive performance test results at each time point will be produced on FAS.

#### **10.4 EXPOSURE TO STUDY TREATMENT**

Treatment duration (days) as defined in section 8.5 will be listed and summarized on SAF using descriptive statistics for continuous variables, by treatment group

#### **10.5 COMPLIANCE WITH STUDY TREATMENT**

Compliance data will be summarized on SAF using descriptive statistics for categorical data as defined in Section 4.2.1.

A listing of compliance will be provided on SAF.

#### **10.6 TRIAL DISCONTINUATION**

A summary of reasons for premature trial discontinuation will be provided for the RAN. The summary table will be presented in descending order in the active treatment group (i.e., the reason with the highest number of occurrences appears first). A listing of subjects who did not complete the study (see section 8.7) will be provided.

#### **10.7 PRIMARY EFFICACY ENDPOINT**

The primary analysis will be performed according to the intent-to-treat (ITT) principle on the FAS.

### 10.7.1 Statistical model and hypotheses

The null hypothesis is that active MM-120 is not better than placebo; this will be rejected with a one-sided p-value < 0.10 with 80% power if the true efficacy of MM-120 reaches a standardized mean improvement over placebo of 0.60.

### 10.7.2 Main analysis

#### 10.7.2.1 Estimand

The primary estimand quantifies the treatment effect of MM-120 at 6-weeks vs placebo after twice weekly administration while accounting for intercurrent events (IEs) with potential confounding effects and IEs leading to study discontinuation prior to the 6-week assessment.

The following attributes describe the primary estimand:

- Population: Subjects in the FAS
- Endpoint: Change from baseline to Week 6 in the AISRS Score
- Treatment of interest: the randomized treatment MM-120 or placebo as a twice weekly treatment.
- Handling of intercurrent events (IEs) prior to AISRS assessments.

Depending on the IE causing the missing or potentially biased value, two sequential policy strategies will be applied:

1. Policy strategy. Available data will be used; missing data will be imputed under a Missing At Random (MAR) assumption by borrowing information from subjects in the same treatment group in following cases:
  - IEs related to COVID-19 pandemic and other intercurrent missing data (see details in Section 10.7.2.1.1).
2. Policy strategy. Available data recorded after the IE will be set to missing; such missing data will be imputed/substituted under a Missing Not At Random (MNAR) assumption by borrowing information from the placebo arm subjects (reference-based imputation) in following cases:
  - Intake of prohibited medications/therapies with potential confounding effect (APPENDIX C) (see details in Section 10.7.2.1.1).
  - Other IEs leading to treatment/study discontinuation (except those related to COVID-19 pandemic (see details in Section 10.7.2.1.1)).

- Summary measure: Difference between MM-120 and placebo in mean change from baseline to Week 6 for AISRS Score.

